5.3.3.3. Treatment after Initial Evidence of Radiologic Disease Progression

Immunotherapeutic agents such as avelumab may produce antitumor effects by potentiating endogenous cancer-specific immune responses. The response patterns seen with such an approach may extend beyond the typical time course of responses seen with cytotoxic agents, and can manifest as a clinical response after an initial increase in tumor burden or even the appearance of new lesions.

If radiologic imaging shows disease progression, tumor assessment should be repeated ≥ 4 weeks later in order to confirm the observation, unless clinical deterioration occurs. Assigned study treatment may be continued at the investigator's discretion while awaiting radiologic confirmation of disease progression.

Patients may receive study treatment while waiting for confirmation of PD if they are clinically stable as defined by the following criteria:

- Absence of clinical signs and symptoms (including worsening of laboratory values) of disease progression.
- No decline in ECOG performance status.
- Absence of rapid progression of disease by radiographic imaging.
- Absence of progressive tumor at critical anatomical sites (eg, cord compression) requiring urgent alternative medical intervention.

If repeat imaging no longer shows PD but rather CR, PR or SD compared to the initial scan, treatment may be continued/resumed. In determining whether or not the tumor burden has increased or decreased, investigators should consider all target as well as non target lesions.

If the repeat imaging confirms PD, patients should be discontinued from study treatment. However, according to the investigator's clinical judgment and after discussion between the investigator and the sponsor, if a patient with evidence of PD is still experiencing clinical benefit, the patient may be eligible for continued treatment with single agent avelumab, axitinib, or avelumab combined with axitinib. The investigator's judgment should be based on the overall benefit-risk assessment and the patient's clinical condition, including performance status, clinical symptoms, adverse events and laboratory data.

Patients who stop avelumab after initial clinical benefit while on treatment and then experience radiologic disease progression thereafter will be eligible for re-treatment with avelumab at the discretion of the investigator and after discussion with the sponsor's medical monitor if 1) no cancer treatment was administered other than axitinib since the last dose of avelumab, 2) the patient does not meet the safety withdrawal criteria, and 3) the trial is still open. Patients will resume avelumab therapy at the same dose and schedule applied at the time of discontinuation.

5.3.4. Food Requirements

Both investigational products may be administered without regard for food, but patients must avoid foods that are known strong CYP3A4/5 inhibitors (eg, grapefruit juice or grapefruit/grapefruit-related citrus fruits [eg, Seville oranges, pomelos]).

5.3.5. Recommended Dose Modifications

Every effort should be made to administer investigational product on the planned dose and schedule.

In the event of significant toxicity, dosing may be delayed and/or reduced as described below. In the event of multiple toxicities, dose modification should be based on the worst toxicity observed. Patients are to be instructed to notify investigators at the first occurrence of any adverse symptom. In addition to dose modifications, investigators are encouraged to employ best supportive care according to local institutional clinical practices and according to the guidance for selected adverse events provided below.

For axitinib dose modifications may occur in 2 ways:

- Within a cycle: dosing interruption until adequate recovery and dose reduction, if required, during a given treatment cycle;
- In the next cycle: dose reduction may be required in a subsequent cycle based on toxicity experienced in the previous cycle.

For avelumab, no dose modifications are permitted in this study, but next infusion may be omitted based on persisting toxicity, as outlined in [Table 5](#).

Dose modifications and infusion omissions may occur independently for the two drugs used in this study and will be reported in the CRF.

Available axitinib dose levels for inpatient dose modification are listed in [Table 4](#).

5.3.5.1. Inpatient Axitinib Dose Escalation and Dose Reduction

In the Dose Finding Phase, inpatient axitinib dose escalation is not permitted for patients treated at DL-1A.

Inpatient axitinib dose escalation is permitted for patients treated in the Dose Finding Phase at DL-1B (avelumab 10 mg/kg Q2W + axitinib 3 mg BID). In these patients, after the completion of the primary DLT observation period (4 weeks), inpatient axitinib dose escalation to 5 mg BID may occur according to the criteria reported below.

In the Dose Expansion Phase, inpatient axitinib dose escalation up to 10 mg BID may occur according to the criteria reported below.

Criteria for Inpatient Dose Escalation: Patients who tolerate the current axitinib dose without Grade >2 drug-related adverse events for 2 consecutive weeks (in the Dose Expansion Phase) or 4 consecutive weeks (in the Dose Finding Phase, only DL-1B), and who do not experience BP >150/90 mm Hg or concurrent administration of antihypertensive medication, have the option to have their axitinib dose increased (by one dose level at a time [Table 4]). Patients treated in the Dose Finding Phase at DL-1B have the option to have their axitinib dose increased to a maximum dose of 5 mg BID. Particular attention should be provided to a patient's overall safety profile prior to implementing inpatient axitinib dose escalation.

Table 4. Axitinib Dose Levels

Dose Level	Dose
+2	10 mg BID
+1	7 mg BID
Starting Dose	5 mg BID
-1	3 mg BID
-2	2 mg BID

Patients will be monitored closely for toxicity, and axitinib treatment may be adjusted by dosing interruption with or without dose reduction as indicated in Table 4. Dosing interruption and/or dose reduction by 1, and if needed, up to 2 dose levels (one dose level reduction at a time) will be allowed depending on the type and severity of toxicity encountered. Management of patients requiring more than 2 dose reductions should be discussed with the sponsor's medical monitor.

Patients who have undergone dose reduction may also undergo dose re-escalation back to the previous dose level at the discretion of the Investigator in the absence of Grade \geq 2 non-hematologic treatment-related toxicity for at least 28 days.

5.3.5.2. Management of Axitinib-Related Hypertension

Patients will be issued BP cuffs (provided by the sponsor) for home monitoring and instructed to measure their BP twice daily, prior to taking each axitinib dose. All BP measurements will be recorded in a diary and brought to the nurse or study coordinator at each clinic visit. Patients should be instructed to contact the site immediately for guidance if their systolic blood pressure rises above 150 mm Hg, diastolic blood pressure rises above 100 mm Hg, or if they develop symptoms perceived to be related to elevated blood pressure

(eg, headache, visual disturbances), although a different blood pressure threshold for contacting the site may be used according to the investigator's clinical judgment.

Blood pressure should be well-controlled prior to initiating axitinib, and patients should be monitored for hypertension. To treat an increase in BP, standard antihypertensives may be used (for example, thiazide or thiazide-like diuretics, angiotensin II receptor blockers, angiotensin converting-enzyme inhibitors, and dihydropyridine [DHP] calcium channel blockers.^{33,34}

5.3.5.3. Axitinib Dose Modifications and Avelumab Infusion Omissions for Treatment-Related Toxicity

Recommended axitinib dose modifications and avelumab infusion omissions in case of drug-related toxicity are shown in [Table 5](#). These guidelines might be further modified at the discretion of the sponsor based on the emerging safety profile of the combination. The investigator should discuss with the sponsor's medical monitor any dose modification and or treatment discontinuation in case of persistent toxicity that would lead to dose modification or treatment discontinuation per toxicity management guidelines. Consult with the sponsor's medical monitor before discontinuing the patient.

Consider consulting with the sponsor's medical monitor for Grades 1 and 2 drug-related toxicities ([Table 5](#)), and always consult with the sponsor's medical monitor for Grades 3 and 4 drug-related toxicities ([Table 5](#)).

Table 5. Axitinib Dose Modifications and Avelumab Infusion Omissions for Investigational Product-Related Toxicity

Toxicity	NCI CTCAE Severity Grade	Axitinib	Avelumab
		Dose Modification	Treatment Modification
Hematologic Abnormalities	Grade 1	
 Continue at the same dose level. 	
 Continue as per schedule.
	Grade 2	
 Continue at the same dose level. 	
 Continue as per schedule.
	Grade 3	
 Continue at the same dose level. 	
 Withhold avelumab Re-initiate avelumab once toxicity is Grade \leq1 or baseline. Permanently discontinue avelumab if toxicities does not resolve to Grade \leq1 or baseline within 12 weeks (consult with the sponsor's medical monitor before permanently discontinuing the treatment). 
 Exceptions are: Laboratory values that do not have any clinical correlate.
	Grade 4	
 Withhold until recovery to Grade \leq2. Then, reduce by 1 dose level and resume treatment. For Grade 4 lymphopenia not associated with clinical events (eg, opportunistic infection) axitinib treatment may continue without interruption. 	
 Permanently discontinue avelumab (consult with the sponsor's medical monitor before permanently discontinuing the treatment). 
 Exceptions are: Laboratory values that do not have any clinical correlate.
Proteinuria	Dipstick negative or shows 1+ (Grade 1)	
 Continue at the same dose level. 	
 Continue as per schedule.
	If dipstick shows >1+, perform 24 hour urine collection. Dosing may continue while waiting for test results.		
	<2 g proteinuria/24 hour	
 Continue at the same dose level. 	

090177e1907c3de0\0.1\Draft\Versioned On:01-Mar-2019 17:22 (GMT)

Toxicity	NCI CTCAE Severity Grade	Axitinib	Avelumab
		Dose Modification	Treatment Modification
	≥2 g proteinuria/ 24 hours	
 Withhold until proteinuria is <2 g/24 hours. Repeat 24-hour urine collection for proteinuria and creatinine clearance (interval at investigator discretion) until proteinuria is <2 g/24 hours. Then, resume at the same dose level or reduce by 1 dose level as per investigator judgment. 	
Hypertension	2 systolic BP readings separated by at least 1 hour show systolic pressure ≤150 mm Hg (one or both readings) And 2 diastolic BP readings separated by at least 1 hour show diastolic pressure ≤100 mm Hg (one or both readings)	
 Continue at the same dose level See Section 5.3.5.2 for monitoring/management of axitinib-related hypertension. 	
 Continue as per schedule
	2 systolic BP readings separated by at least 1 hour show systolic pressure >150 mm Hg OR 2 diastolic BP readings separated by at least 1 hour show diastolic pressure >100 mm Hg	
 If not on maximal antihypertensive treatment, institute new or additional antihypertensive medication and continue at the same dose level. If on maximal antihypertensive treatment, reduce by 1 dose level. See Section 5.3.5.2 for monitoring/management of axitinib-related hypertension. 	
 Continue as per schedule.

090177e1907c3de0\0.1\Draft\Versioned On:01-Mar-2019 17:22 (GMT)

090177e1907c3de0\0.1\Draft\Versioned On:01-Mar-2019 17:22 (GMT)

Toxicity	NCI CTCAE Severity Grade	Axitinib	Avelumab
		Dose Modification	Treatment Modification
	2 systolic BP readings separated by at least 1 hour show systolic pressure >160 mm Hg OR 2 diastolic BP readings separated by at least 1 hour show diastolic pressure >105 mm Hg	
 Withhold until BP is less than 150/100 mm Hg¹ and adjust antihypertensive medication. Then, reduce by 1 dose level and resume treatment. ¹ If axitinib dosing is temporarily discontinued, patients receiving antihypertensive medications should monitor closely for hypotension. The plasma half-life of axitinib is 2-4 hours and BP usually decreases within 1-2 days following dose interruption. See Section 5.3.5.2 for monitoring/management of axitinib-related hypertension 	
 Continue as per schedule.
	Recurrent hypertension following previous dose reduction (2 systolic BP readings separated by at least 1 hour show systolic pressure >150 mm Hg) OR Recurrent diastolic BP >100 mm Hg (2 BP readings separated by at least 1 hour) following previous dose reduction	
 Repeat dose reduction by one lower dose level. See Section 5.3.5.2 for monitoring/management of axitinib-related hypertension. 	
 Continue as per schedule.
Infusion-related Reaction	Grade 1-4	
 Continue at the same dose level. 	
 See Section 5.3.5.5 and Table 6
Hypersensitivity reactions	Grade 3-4	
 Continue at the same dose level. 	
 See Section 5.3.5.6 and Table 6
Tumor lysis syndrome	Grade 1-4	
 See Other Non-Hematologic Toxicities and/or Laboratory Abnormalities. 	
 See Section 5.3.5.7 and Figure 1

Toxicity	NCI CTCAE Severity Grade	Axitinib	Avelumab
		Dose Modification	Treatment Modification
Immune-related AE (irAE)	Grade 1-4	
 Grade 1: continue at the same dose level Grade 2-4: hold treatment until recovery to Grade \leq1 and restart axitinib at the same dose level for Grade 2 and at reduced dose level for Grade 3-4. 	
 See Section 5.3.5.8 and Table 7
Other Non-hematologic Toxicities and Laboratory Abnormalities	Grade 1	
 Continue at the same dose level. 	
 Continue as per schedule.
	Grade 2	
 Continue at the same dose level. 	
 Continue as per schedule.
	Grade 3	
 Reduce by 1 dose level. Grade 3 toxicities controlled with symptomatic medications, or Grade 3 asymptomatic biochemistry laboratory abnormalities: continue at the same dose or reduce by 1 dose level as per investigator judgment. 	
 Withhold avelumab. Re-initiate avelumab once toxicity is Grade \leq1 or baseline. Permanently discontinue avelumab if toxicity does not resolve to Grade \leq1 or baseline value within 12 weeks (consult with medical monitor before permanently discontinuing the treatment). 
Exceptions are:
 
 Laboratory values that do not have any clinical correlate (eg, amylase or lipase abnormality that is not associated with symptoms or clinical manifestations of pancreatitis). Nausea and vomiting controlled by medical therapy. Tumor flare phenomenon defined as local pain, irritation, or rash localized at sites of known or suspected tumor.

090177e1907c3de0\0.1\Draft\Versioned On:01-Mar-2019 17:22 (GMT)

Toxicity	NCI CTCAE Severity Grade	Axitinib	Avelumab
		Dose Modification	Treatment Modification
	Grade 4	
 • Hold treatment until recovery to Grade \leq2. • Then, reduce by 1 dose level and resume treatment. • Grade 4 asymptomatic biochemistry laboratory abnormality: study treatment may continue without interruption. 	
 • Permanently discontinue avelumab (consult with the sponsor's medical monitor before permanently discontinuing the treatment). 
Exceptions are:
 
 • Laboratory values that do not have any clinical correlate.

090177e1907c3de0\0.1\Draft\Versioned On:01-Mar-2019 17:22 (GMT)

5.3.5.4. Special Precautions for Avelumab Administration

In order to mitigate avelumab infusion-related reactions, a premedication with an antihistamine and with paracetamol (acetaminophen) approximately 30 to 60 minutes prior to each dose of avelumab is mandatory (for example, 25-50 mg diphenhydramine and 500-650 mg paracetamol [acetaminophen] IV or oral equivalent). This may be modified based on local treatment standards and guidelines, as appropriate.

As with all monoclonal antibody therapies, there is a risk of allergic reactions including anaphylactic shock. Avelumab should be administered in a setting that allows for immediate access to an intensive care unit or equivalent environment and administration of therapy for anaphylaxis, such as the ability to implement immediate resuscitation measures. Steroids (dexamethasone 10 mg), epinephrine (1:1,000 dilution), allergy medications (IV antihistamines), bronchodilators, or equivalents, and oxygen should be available for immediate access.

Infusion of avelumab will be stopped in case of Grade ≥ 2 infusion-related, allergic, or anaphylactic reactions. If an allergic reaction occurs, the patient must be treated according to the best available medical practice. Guidelines for the emergency treatment of anaphylactic reactions are available at www.resus.org.uk/pages/reaction.pdf (Working Group of the Resuscitation Council [United Kingdom]), www.erc.edu (European Resuscitation Council [European Union]), www.heart.org (American Heart Association [United States]), and www.american-cpr.com (American Cardio-Pulmonary Resuscitation [CPR] Training™ [United States]). Patients should be instructed to report any delayed reactions to the investigator immediately.

Treatment recommendations for the management of infusion-related reactions, severe hypersensitivity reactions, tumor lysis syndrome, and immune-related adverse events (irAEs) are outlined in [Section 5.3.5.5](#), [5.3.5.6](#), [5.3.5.7](#), [5.3.5.8](#), respectively.

Investigators should also monitor patients closely for potential irAEs, which may become manifest at any time after the first dose of avelumab treatment. Such events may more often consist of persistent rash, diarrhea and colitis, autoimmune hepatitis, arthritis, glomerulonephritis, cardiomyopathy, or uveitis and other inflammatory eye conditions. However, potential irAEs can occur in any organ or tissue. Treatment recommendations for the management of irAEs are outlined in [Section 5.3.5.8](#).

5.3.5.5. Management of Avelumab Infusion-Related Reactions

Since avelumab is administered IV, infusion-related reactions may occur (with symptoms such as fever, chills, rigors, diaphoresis, and headache). Treatment of the infusion-related reaction and modifications of avelumab infusion are mainly dependent upon severity, as indicated in [Table 6](#).

Table 6. Treatment Modification for Symptoms of Avelumab Infusion -Related Reactions

NCI CTCAE Grade	Treatment Modification for Avelumab
Grade 1 – mild Mild transient reaction; infusion interruption not indicated; intervention not indicated.	Decrease the avelumab infusion rate by 50% and monitor closely for any worsening. The total infusion time for avelumab should not exceed 120 minutes.
Grade 2 – moderate Therapy or infusion interruption indicated but responds promptly to symptomatic treatment (eg, antihistamines, NSAIDs, narcotics, IV fluids); prophylactic medications indicated for ≤24 hours.	Stop avelumab infusion. Resume infusion at 50% of previous rate as soon as infusion-related reaction has resolved or decreased to at least Grade 1 in severity, and monitor closely for any recurrence or worsening.
Grade 3 or Grade 4 – severe or life-threatening Grade 3: Prolonged (eg, not rapidly responsive to symptomatic medication and/or brief interruption of infusion); recurrence of symptoms following initial improvement; hospitalization indicated for clinical sequelae. Grade 4: Life-threatening consequences; urgent intervention indicated.	Stop the avelumab infusion immediately and disconnect bag infusion tubing from the patient. Avelumab treatment must be permanently discontinued.

IV=intravenous, NCI CTCAE=National Cancer Institute Common Terminology Criteria for Adverse Events, NSAIDs=non-steroidal anti-inflammatory drugs.

Once the avelumab infusion rate has been decreased by 50% due to an infusion-related reaction, it must remain so for all subsequent infusions. The total infusion time for avelumab should not exceed 120 minutes.

Additional Modifications for Patients with Grade 2 Infusion-Related Reactions

In the event of a Grade 2 infusion-related reaction that does not improve or worsens after implementation of the modifications indicated in Table 6 (including reducing the infusion rate by 50%), the investigator may consider treatment with corticosteroids, and the infusion should not be resumed for that cycle. At the next cycle, the investigator may consider the addition of H2-blocker antihistamines (eg, famotidine or ranitidine), meperidine, or ibuprofen to the mandatory premedication. Prophylactic steroids are NOT permitted.

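### Section 5.3.5.5 can be read as allowing next-cycle avelumab after infusion reactions that Table 6 defines as Grade 3 and requires to end avelumab for good

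*Protocol*

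**What the plan says.** Protocol Section 5.3.5.5 contains two sets of instructions for infusion-related reactions.

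**Table 6.** Grade 2 is defined by: "Therapy or infusion interruption indicated but responds promptly to symptomatic treatment". The action is to stop the infusion, then: "Resume infusion at 50% of previous rate as soon as infusion-related reaction has resolved or decreased to at least Grade 1 in severity". Sites are next told to "monitor closely for any recurrence or worsening", but the Grade 2 row gives no action if that happens. The Grade 3 definition reads: "Grade 3: Prolonged (eg, not rapidly responsive to symptomatic medication and/or brief interruption of infusion); recurrence of symptoms following initial improvement". For Grades 3 and 4 the instruction is: "Avelumab treatment must be permanently discontinued". Appendix 6 repeats the Grade 3 definition and the discontinuation.

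**The Grade 2 paragraph below Table 6.** It begins: "In the event of a Grade 2 infusion-related reaction that does not improve or worsens after implementation of the modifications indicated in Table 6". It names the 50% rate reduction as one of those modifications, allows corticosteroids, and says "the infusion should not be resumed for that cycle". It continues: "At the next cycle, the investigator may consider the addition of H2-blocker antihistamines", with meperidine or ibuprofen as other options.

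The infusion-reaction row of Table 5 (Section 5.3.5.3) refers the reader to both Section 5.3.5.5 and Table 6 and gives no order of precedence.

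**The concern.** The Grade 2 paragraph is triggered by failure to improve or by worsening after the Table 6 steps. Some reactions that fit this trigger also fit the Table 6 definition of Grade 3. For them the paragraph ends the infusion for one cycle and looks ahead to the next dose, while the Grade 3 row ends avelumab altogether.

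At stake is a mandatory stopping rule. Faced with the same reaction, one site could re-dose at the next cycle and another could stop for good. The first would re-expose a patient whom Table 6 says must not receive avelumab again.

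The label has two further effects. Section 5.3.5.3 makes consultation with the medical monitor obligatory for Grades 3 and 4 but only something to consider for Grades 1 and 2. The investigator assigns the grade (SAP 3.2.1), and the action taken comes from the adverse event page (SAP 6.6.1). Both therefore carry into the SAP 6.6.4 tables of Grade 3 or higher infusion reactions and of infusion reactions leading to avelumab discontinuation.

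**Working it through.** No figure in the plan is in dispute, so the check sets the two rules side by side.

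1. **Reaction that does not settle after the infusion is stopped and drugs are given.** It fails the prompt-response element of the Table 6 Grade 2 definition and meets the Grade 3 example of a reaction not rapidly responsive. It also fits the paragraph's trigger of not improving. Table 6 gives permanent discontinuation; the paragraph gives omission for that cycle, with the next cycle foreseen. The rules conflict.

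2. **Reaction that resolves or clearly improves, then returns after the 50% restart.** Table 6 permits the restart only once the reaction has resolved or fallen to Grade 1, so improvement has already occurred. Return of symptoms then meets the recurrence element of Grade 3. It can also be read as worsening after the rate reduction, which is the paragraph's trigger. The rules conflict.

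3. **Grade 1 reaction slowed by 50% that becomes Grade 2.** Halving the rate is the Table 6 action for Grade 1, so the paragraph's mention of the reduced rate fits. No Grade 3 criterion is met. No conflict.

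4. **Residual Grade 1 symptoms that merely persist after restart.** Table 6 allows a restart with Grade 1 symptoms present. No conflict. If those symptoms worsen without having cleared, it is not clear that this is recurrence: the Grade 2 row names recurrence and worsening separately, while the Grade 3 definition names only recurrence. This case is not counted here.

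5. **Prompt response to drugs, including corticosteroids.** Appendix 6 lists corticosteroids among Grade 2 treatments, so using them does not itself move a reaction to Grade 3. No conflict.

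**Search for a tie-break.** Table 5 cites both places. The introduction to Table 6 says management depends mainly on severity as set out there, which favours Table 6 but does not limit the paragraph below it. The clause allowing changes under local standards (Section 5.3.5.6 and the opening of Appendix 6) attaches to the Appendix 6 recommendations, not to Table 6. No text settles which rule governs cases 1 and 2.

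**Effect on the tables.** One patient moved between Grade 2 and Grade 3 shifts the Grade 3 or higher percentage by 1/n: 1/40 = 2.5 percentage points in the planned expansion cohort and 1/55 = 1.8 points in the planned maximum for both phases (Protocol 9.3; SAP 5.1.1). This holds for any re-graded event and says nothing about how often the wording would mislead.

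**The case against.** The strongest reply is that the paragraph assigns no grade. Its heading confines it to Grade 2; grades come from CTCAE 4.03 and the definitions in Table 6, which Appendix 6 repeats. Read together, a reaction meeting a Grade 3 criterion leaves the paragraph's scope, and a site would have to disregard a definition printed twice in order to re-dose. Next-cycle dosing is implied by the premedication sentence, not ordered.

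Much of this stands. The paragraph does not itself speak of recurrence or of slow response; those terms are Table 6's. It also has proper uses, shown in cases 3 to 5. A reader might infer that every reaction it covers is really Grade 3, and those cases show otherwise.

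The reply does not remove cases 1 and 2. The paragraph keeps the Grade 2 label while describing a reaction that has failed the Table 6 steps, and it never tells the site to re-grade. Because the Grade 2 row of Table 6 gives no action on recurrence, the paragraph is the natural place to look for one.

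Two further limits are fair. Care within the cycle need not differ, since the infusion stops under either rule; only later doses are at issue. Section 5.3.5.3 also asks investigators, without a grade limit, to discuss dose modification for persistent toxicity with the medical monitor, so consultation is weakened, not absent.

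**Conclusion.** The point holds as an internal inconsistency. The Grade 2 paragraph can be read as covering, and foreseeing further avelumab for, two kinds of reaction that Table 6 and Appendix 6 define as Grade 3 with mandatory permanent discontinuation: those not rapidly responsive to stopping and symptomatic treatment, and those that resolve or clearly improve and then recur after the 50% restart. It should be fixed because it blurs a safety-stopping rule.

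The conclusion rests on the wording alone. How many patients are affected is unknown: the documents give no frequency for such reactions and none is assumed.

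A reader might also infer that the ambiguity disturbed the DLT count or the MTD, because a non-hematologic Grade 3 toxicity inside the four-week window is in general a DLT (Section 3.1.2). The documents do not support that. They report no such reaction among the dose-finding patients, and SAP Section 6 states only that dose finding was complete, with DL1 the only level tested, with and without lead-in.

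**What to change.** Add to the Grade 2 paragraph in Section 5.3.5.5:

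> This paragraph applies only to reactions that still meet the Table 6 Grade 2 definition. A reaction that meets any Table 6 Grade 3 criterion, including recurrence of symptoms after restart at the 50% rate, is graded as Grade 3, avelumab is permanently discontinued and the medical monitor is consulted.

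Optionally, before the SAP 6.6.4 tables are produced, query the recorded grade and action for every infusion reaction whose action on the adverse event page is interruption or withdrawal of the drug (SAP 6.6.1 and 6.6.1.3). Run the query before the SAP 6.6.1.3 exclusions, which drop some reactions with at least 90% of the dose given and no later delay. The exposure flags alone are not enough: SAP 6.5.3.3 finds doses below 90% of plan and SAP 6.5.3.8 finds infusions stopped and restarted the same day, so an infusion stopped at 90% or more and never restarted escapes both.

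The cost is two sentences of protocol text and, if adopted, a short data query. The clinical downside is that a few patients who might have tolerated re-challenge will stop avelumab; Protocol Section 3.1 lets them continue axitinib alone.
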